5.0 Randomization and Blinding

This is a randomized, double-blind, placebo-controlled study with an open-label cross-over segment. For Stage 1, a randomization list will be prepared at the beginning of the study. If needed, subsequent randomization lists will be created to replace subjects who withdraw from the study to ensure that replacement subjects are not added to the end of the initial list. Each subject will be assigned to one of the two dose conditions: 0 mg (placebo) or 125 mg (full dose). Eight evaluable subjects will be assigned to the full dose condition, and four to the placebo condition. The study will employ a blinded randomization procedure that will maintain the 8:4 ratio while maintaining the blind and ensuring that each subsequent condition assignment is not predicated on the previous assignment.

6.0 Sample Size and Power Considerations

This study is a pilot investigation intended to gather preliminary data on the safety and efficacy of MDMA in 12 subjects on the autism spectrum with social anxiety. Because of their exploratory nature, pilot studies are often not powered for detecting the desired effect. Because it is a pilot study in a small sample, results will be used to collect effect size estimates for statistical power calculations for adequately powered subsequent studies.

7.0 Measures

7.1 Outcome Measures

- Liebowitz Social Anxiety Scale (LSAS), total score
- Perceived Stress Scale (PSS), total score
- Beck Depression Inventory-II (BDI-II), total score
- Interpersonal Reactivity Index (IRI), composite scores
- Rosenberg Self Esteem Scale (RSES), total score
- State Trait Anxiety Index (STAI), composite scores
- The Awareness of Social Inference Test (TASIT), composite and total scores
- Toronto Alexithymia Scale 20 (TAS-20), total score
- Emotional Regulation Questionnaire (ERQ), composite scores

- Quality of Life Questionnaire (QoL-Q), composite and total scores

7.2 Safety Measures

- Columbia Suicide Severity Rating Scale (C-SSRS)
- Subjective Units of Distress (SUD)
- General Well-being (GWB)
- Symptoms Specific to Population
- Vital signs (systolic blood pressure (SBP), diastolic blood pressure (DBP), heart rate (HR), body temperature (BT))
- Adverse Events (AE), including Spontaneously Reported Reactions (SRR)

7.3 Process Measures

- Belief of Treatment Group Assignment
- Subject perceptions of Experimental Sessions
- Feedback Questionnaire

8.0 Analyses

In general, nominal variables will be described in terms of frequencies and percentages and analyzed using chi square analysis. Ordinal and non-normal continuous variables will be described using sample median and range, and analyzed by non-parametric statistical tests, and approximately normal variables will be described using sample mean and standard deviations and analyzed by parametric statistical tests. All statistical tests will be two-sided. All p-values will be rounded to and displayed in four decimals. If a p-value less than 0.0001 occurs it will be shown in tables as <0.0001. For any analysis that is called out as parametric, e.g. t-test, the parametric assumptions will be examined. If necessary, nonparametric analyses will be utilized, e.g. Wilcoxon rank-sum test.

Clinical data will be presented in tabular format. Data not subject to analysis according to this plan will not appear in any tables or graphs, but will be included in the data listings. Analyses will be carried out with SAS Version 9.3 or higher. Selected results may be presented graphically using standard graphical software.

Post-hoc exploratory analyses not identified in this SAP may be performed to further examine the study data. These analyses will be clearly identified as such in the final clinical study report.

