The main estimates of effect size from blinded data will be conducted after the outcome measure assessments at the six-month follow-up are complete for all subjects. Data from all doses of MDMA during Stage 1 (n=16), to be compared with all data from placebo sessions (n=8), with each experimental session treated as an independent observation. The MDMA condition will encompass both Group 1 and Group 2 MDMA doses. Estimates of effect size will be obtained from BDI-II, STAI, PSS, IRI, RSES, ERQ, TAS-20, and QoL-Q scores collected pre-treatment, during and after each experimental session, and the follow-up period, with p value set at 0.05. Effect size will be used to determine the appropriate sample size for future studies.

Scores for BDI-II, STAI, PSS, IRI and RSES completed after each of the experimental session will be averaged to produce mean scores for these periods, including a post-experimental session 1 and post-experimental session 2 average score. BDI-II, STAI and PSS scores gathered via postal mail at monthly intervals from two to five months after the second experimental session will be averaged to produce mean scores for the follow-up period. Missing responses will be replaced with the sample average. These averages will be used for estimates of effect size.

TASIT scores will be compared assessing baseline, after experimental session 1, after experimental session 2, at integrative session six and at 6-month follow up. Correlations between TASIT scores and LSAS scores at the time point following each TASIT score will be made to see whether increased awareness of social cues is associated with reduced social anxiety. MDMA dose will be used as a covariate in order to examine the potential relationship between dose and changes in one or more variable, with dose (75, 100 or 125 mg) serving as the covariate.

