2.0 Introduction

This document presents a Statistical Analysis Plan (SAP) for MAPS study protocol MAA-1, a Phase 2 pilot clinical trial designed to evaluate the safety, feasibility, and efficacy of MDMA-assisted psychotherapy in treating social anxiety in adults on the autism spectrum.

The Multidisciplinary Association for Psychedelic Studies (MAPS) is a non-profit research and educational organization working to obtain approval for the prescription use of 3,4-methylenedioxymethamphetamine (MDMA)-assisted psychotherapy in adults on the autism spectrum with social anxiety. This is an initial pilot study to assess the efficacy of MDMA for this indication, following promising results from MAPS-sponsored studies of MDMA-assisted psychotherapy for posttraumatic stress disorder (PTSD).

The Phase 2 pilot study will examine the safety, feasibility, and efficacy of MDMA-assisted psychotherapy for social anxiety in 12 MDMA-naïve adults on the autism spectrum. This study is designed as a dose escalation study to assist with the exploration of safety and finding the most effective dose in this population. Subjects assigned to the MDMA group will receive two of three different doses, either 75 mg, 100 mg, or 125 mg MDMA. Overall, eight subjects (66.7%) will be randomized to the MDMA group and four subjects (33.3%) will be randomized to the placebo group. Subjects who received the placebo during Stage 1 will have the opportunity to cross over and take part in a second study segment, referred to as Stage 2, with two open-label experimental sessions, after completing the six-month follow-up visit at the end of Stage 1.

This study is designed to obtain safety data, and secondarily estimates of effect size for efficacy. The data will be used to determine study design and dosing for future studies for this indication. MAA-1 is also intended to contribute to the development of a manualized psychotherapeutic approach to this potential treatment. This study is exploratory. As a result, the sponsor will perform tests on all statistical comparisons without correcting for multiple comparisons.

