8.10.1 Primary Efficacy Analyses

Liebowitz Social Anxiety Scale (LSAS)

The primary efficacy evaluation is the change from baseline to the primary outcome timepoint (visit 13, one month post experimental session 2) in the LSAS score of Social Anxiety (difference score). The primary efficacy comparison on difference scores will be made with independent sample t-tests at an alpha level of 0.05. If the primary hypothesis rejects, pairwise comparisons among the treatment groups will be made with t-tests. If the parametric assumptions for the t-test analyses are not met, the analogous nonparametric methods will be used (Wilcoxon Rank Sum Test). If data has normal distribution, Cohen's d placebo-subtracted effect size will be estimated on mean difference scores from baseline to Visit 13 with confidence intervals.

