8.10.3.1 Process Measures

Belief of Treatment Group Assignment

In order to compare the therapists’, independent raters’, and subjects’ belief of treatment group to actual dose received in each blinded session, the number and frequency of correct guesses will be calculated and depicted by treatment group and study role (subject, therapist, or independent rater).

Feedback Questionnaire

The Feedback Questionnaire nominal variables will be described in terms of frequencies and percentages, while ordinal and non-normal continuous variables will be described using sample mean, standard deviations, and range.

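### SAP 8.0 makes chi-square the default test for nominal variables, but with 8 versus 4 subjects its large-sample condition fails in every 2x2 table and no exact fallback is named (minor)

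*SAP*

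**What the plan says.** SAP 8.0 (Analyses) sets a general rule: "nominal variables will be described in terms of frequencies and percentages and analyzed using chi square analysis". It adds that "All statistical tests will be two-sided" and that p-values are shown to four decimals. Its one fallback concerns analyses named as parametric, where a rank test may replace a t-test. Neither document names Fisher's test or any other exact test, gives a rule for small expected counts, or says whether chi-square carries a continuity correction.

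On sample size, SAP 2.0 states that "eight subjects (66.7%) will be randomized to the MDMA group and four subjects (33.3%) will be randomized to the placebo group". On testing in general, the same section says that "the sponsor will perform tests on all statistical comparisons without correcting for multiple comparisons". A 0.05 level appears in SAP 8.10.1 ("independent sample t-tests at an alpha level of 0.05") and in protocol section 12.0 ("with p value set at 0.05"). Neither place ties that level to chi-square, so using 0.05 for nominal variables is an assumption, though a natural one.

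**The concern.** The chi-square p-value is a large-sample approximation. The SAP provides for failed assumptions with continuous data but not with nominal data, where the failure is fixed by the design before any data arrive. With four placebo subjects, a result can pass 0.05 on very few events: none in 8 on MDMA against 2 in 4 on placebo gives an uncorrected p of 0.0285. Printing such a value to four decimals suggests a precision that the approximation does not have. What is at stake is whether a nominal difference between the arms, if tested, is called significant, and whether that label then influences how the pilot is read when later studies are planned.

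**Working it through.** The documents give no p-value, error rate or power for a nominal comparison, so there is no stated figure to reproduce.

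**Inputs.** MDMA n = 8 and placebo n = 4 (SAP 2.0); two-sided tests (SAP 8.0); level 0.05 (assumed, as in SAP 8.10.1).

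**Expected counts.** With *m* events among 12 subjects, the smaller placebo cell has expected count 4 × min(*m*, 12 − *m*)/12. It is largest at *m* = 6: 4 × 6/12 = 2. With more than two categories, each placebo cell has expected count 4*m*/12, which is below 4 whenever *m* < 12. Counting sessions (16 versus 8) does not rescue the condition: the smallest expected count is then at most 8 × 12/24 = 4, still below 5.

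**Enumeration.** There are 9 × 5 = 45 possible tables. Leaving out the two with no events or all events leaves 43. For *a*/8 versus *b*/4, with *m* = *a* + *b*, uncorrected Pearson X² = 12[*a*(4 − *b*) − *b*(8 − *a*)]² / [8 × 4 × *m* × (12 − *m*)]. Fisher's p sums the hypergeometric probabilities no larger than that of the observed table.

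Worked example, 6/8 versus 0/4:
- X² = 12 × (6 × 4 − 0)²/(8 × 4 × 6 × 6) = 6912/1152 = 6.0, p = 0.0143.
- Fisher: (28 + 28)/924 = 0.0606.

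Worked example, 0/8 versus 2/4:
- X² = 12 × (0 − 16)²/(8 × 4 × 2 × 10) = 3072/640 = 4.8, p = 0.0285.
- Fisher: 6/66 = 0.0909.

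The discordant tables, each with its mirror image:

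| MDMA vs placebo | Mirror | Pearson | Yates-corrected | Fisher |
|---|---|---|---|---|
| 6/8 vs 0/4 | 2/8 vs 4/4 | 0.0143 | 0.0662 | 0.0606 |
| 5/8 vs 0/4 | 3/8 vs 4/4 | 0.0384 | 0.1473 | 0.0808 |
| 7/8 vs 1/4 | 1/8 vs 3/4 | 0.0304 | 0.1296 | 0.0667 |
| 8/8 vs 2/4 | 0/8 vs 2/4 | 0.0285 | 0.1709 | 0.0909 |

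Totals at 0.05: Pearson 14 tables, Fisher 6, Yates-corrected the same 6. Eight tables are significant by Pearson and not by Fisher, and none the other way round. The tests agree in 43 − 8 = 35 tables.

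**Actual type I error of uncorrected Pearson.**
- Given the event total: 6/66 = 9.1% for 2 or 10 events; between 6.1% and 8.1% for 4 to 8 events; 1.8% for 3 or 9; zero for 1 or 11.
- Unconditionally, maximum at an event rate of 0.5. The seven rejecting tables on one side contribute 6 + 4 + 1 + 32 + 8 + 28 + 56 = 135, so the size is 2 × 135/4096 = 6.6%. At an event rate of 0.1 it is 2.4%, and at 0.2 it is 4.5%.

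**Fisher's maximum unconditional size:** 0.7%.

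**Where the rule would apply.**
- SAP 8.7 (disposition) rules out inferential tests.
- SAP 8.8 (demographics) is descriptive.
- SAP 8.10.3.1 says of treatment guesses that "the number and frequency of correct guesses will be calculated and depicted by treatment group and study role"; nominal feedback items get frequencies and percentages.
- SAP 8.10.4 asks for counts and incidence of adverse events, C-SSRS responses and vital-sign cutoffs, and names no test.
- SAP 8.10.1 and 8.10.2 use t-tests or Wilcoxon for the primary and secondary endpoints.
- Protocol section 12.0 uses ANOVA for the number and severity of spontaneously reported reactions. It also compares demographic characteristics between the arms, with any difference carried into the safety analyses, and looks at the presence of exacerbated symptoms by arm. It names no test for these last two, so they are the likeliest places for the SAP 8.0 default to be used.

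**The case against.** The strongest reply is that no section pre-specifies a chi-square comparison. This is an exploratory pilot without multiplicity control, and no decision rule depends on a nominal p-value. That stands, and it is why the point is minor. A reader might infer from "the sponsor will perform tests on all statistical comparisons without correcting for multiple comparisons" that safety and blinding conclusions will rest on chi-square p-values. The documents do not support this: that sentence concerns multiplicity, while the sections on adverse events, suicidality and treatment guesses ask only for summaries.

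Second, the discordance depends on which chi-square is meant. With the Yates correction the rejections coincide with Fisher's. This stands as a limit on the size. It also shows an ambiguity to close: 6/8 versus 0/4 is 0.0143 or 0.0662 depending on an unstated option.

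Third, Fisher is not the truth. Across the 14 tables its p is about 2 to 4 times Pearson's, and a reader might conclude that chi-square is wrong by that factor. That goes too far, because Fisher's size never exceeds 0.7% here. Barnard's unconditional exact test with the pooled statistic gives about 0.02 for 6/8 versus 0/4 and 0.043 for 7/8 versus 1/4. Pearson's unconditional excess over 5% is at most 1.6 percentage points. Chi-square is better called unsupported by its own condition than simply invalid. What remains is that the SAP names a test whose condition cannot be met and offers nothing in its place.

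**Conclusion.** The point holds as a minor defect in SAP 8.0. The expected-count condition fails in all 43 tables whichever version of chi-square is meant. The numerical consequence assumes the uncorrected Pearson test, a 0.05 level and all 12 subjects analysed in arms of 8 and 4. Under those assumptions, 8 of 14 nominally significant tables would not be significant by Fisher's test, and type I error reaches 9.1% given the event total and 6.6% unconditionally. No pre-specified efficacy, safety or blinding analysis is shown to depend on it. It matters only where the sponsor chooses to test a nominal comparison, most plausibly the protocol's demographic homogeneity check, and even there SAP 8.8 is descriptive.

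**What to change.** In SAP 8.0, replace chi-square with Fisher's exact test (Fisher-Freeman-Halton for larger tables) as the single governing p-value for nominal comparisons between the arms. State that the subject, not the session or the guess, is the unit, and report the risk difference with an exact confidence interval. Alternatively, state that nominal comparisons are descriptive only, which matches most of the later SAP sections.

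Do not add a mid-p value as a second verdict. It falls below 0.05 in the same 14 tables as uncorrected chi-square, with the same 6.6% maximum size, so it would contradict Fisher in exactly the disputed tables.

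The cost is one sentence of SAP text and one option in the SAS code. The downside is conservatism: for more events on MDMA, Fisher reaches 0.05 only at 7/8 versus 0/4, 8/8 versus 0/4 or 8/8 versus 1/4. That is a further reason to read the interval rather than the p-value.

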2.4 Rationale of Dose Selection

The MDMA doses of 75mg and 125mg to be used in this study have been used in previous and ongoing MAPS-sponsored studies in the U.S., Switzerland, and Israel [81, 82]. Previous researchers have also used doses within this range up to 225mg [75, 76, 78, 79, 91, 99, 116, 124-126]. Prior to the scheduling of MDMA, similar doses and regimens were used in psychotherapy [36, 62, 64]. Each MDMA dose is expected to produce the commonly reported effects of MDMA.

Anecdotal reports suggest a potential for increased sensitivity to the effects of MDMA in autistic individuals who experience sensory hyperarousal [68]. Therefore, subjects will only receive a single administration of MDMA during experimental sessions, and the lower 75 mg and 100 mg doses will be administered to assess for enhanced sensitivity during the first experimental session to subjects randomized to MDMA. MDMA subjects will only escalate to a 25mg higher dose in the second experimental session that they receive one month later. If any subjects within each dose group experience a drug-related SAE, the dose escalation procedure will not continue for remaining subjects in the same dose group in the interest of subject safety. If this occurs, the institutional Data Safety Monitor and Sponsor Medical Monitor will be consulted to determine the course of action. Any subject who experiences a drug-related SAE will be excluded from any additional experimental sessions, but will continue with non-drug therapy and follow-up assessments whenever possible.

Table 1. Dose Regimen

Group # /Randomization /Sample	Stage 1		Stage 2 Open-Label Extension	
	Session 1 Month 1	Session 2 Month 2	Session 1 Month 6	Session 2 Month 7
Group 1 active N=4	75 mg	100 mg	N/A	N/A
Group 1 placebo N=2	Placebo	Placebo	75 mg	125 mg
Group2 active N=4	100 mg	125 mg	N/A	N/A
Group 2 placebo N=2	Placebo	Placebo	75 mg	125 mg

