8.5 Adverse Event Collection

The PI will be responsible for reviewing and confirming all AEs and SAEs collected during the study. The co-therapist or PI will collect AEs during study visits after enrollment.

All SAEs will be collected for the duration of the protocol. All SAEs which occur during the course of the trial, whether considered to be associated with the study drug or not, have to be reported within 24 hours of the CI's awareness of their occurrence. All SAE reports should be faxed to the sponsor. A fax number will be provided to the site in separate site-specific instruction for SAE reporting. In addition to the fax, the PI, or designee should call the Clinical Research Associate (CRA) during normal working hours and verbally inform the CRA of the SAE. During off business hours or if medical advice is needed immediately, the sponsor Medical Monitor will be called. SAE reporting instructions with all contact numbers will be provided to the site prior to study start.

The following symptoms will be assessed at baseline and exacerbations during the study will be tracked and categorized as mild, moderate, or severe on a separate Symptoms CRF log page: Persistent feelings of alienation, Rigidity, Tremor, Dystonic Symptoms, Akathisia, Increased Motor Activity, Decreased Motor Activity, Sensory Hyperarousal, Excitement/Agitation.

AEs to be collected during the study are:

- Serious Adverse Events (SAEs) will be collected from enrollment through termination.
- All AEs and spontaneously reported reactions will be collected on the day of and seven days after each experimental session or until they resolve.

- AEs requiring medical attention, including a doctor visit or treatment with prescription medication, will be collected from the first experimental session through the final integrative session after the second experimental session.
- AEs related to planned treatments or physician visits for baseline conditions collected in the Medical History will not be collected unless there is an exacerbation of the condition.
- Any AE leading to withdrawal will be collected throughout the study.
- All AEs related to changes in psychiatric status will be collected throughout the study.
- Any exacerbations of Symptoms recorded at Medical History will be collected throughout the study.

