Descriptive statistics will be computed for vital signs and subjective distress during each experimental or open-label session. The sponsor will compare pre-drug and post-drug peak blood pressure, heart rate, and body temperature during and after all experimental sessions by condition and MDMA dose. Analyses will compare peak vital signs between MDMA and placebo subjects, and a separate analysis will consider the effects of dose (0, 75, 100 or 125 mg MDMA) upon vital signs.

Frequency tables will be produced on prevalence of spontaneously reported reactions and AEs. Number and severity of spontaneously reported reactions will be compared in MDMA and placebo subjects using a one-way analysis of variance (ANOVA). The effects of MDMA dose upon number and severity of spontaneously reported reactions will also be assessed. Presence and degree of exacerbated symptoms across MDMA and placebo participant will also be examined.

Perceptions of study participation will be examined at baseline, 6-month follow-up, and end of Stage 2 using the Feedback Questionnaire and a qualitative interview. The results of this qualitative analysis will inform the sponsor of expectancies and perceptions about study procedures for future protocol development. Similarly, belief of condition assignments collected during Stage 1 will be used to assess the effectiveness of the double-blind in preparation for future studies. Results from the Feedback Questionnaire and safety data will be utilized to find the appropriate active MDMA dose for future studies.

To facilitate the planning of future studies, a preliminary estimate of effect size may be performed after all the subjects have completed the outcome assessments, one month after the second experimental session, but not all subjects have completed the six-month follow-up evaluation. This preliminary estimate will consist of safety and outcome measures. Results of the preliminary estimate will have no effect on study conduct.

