Vital signs

Vital signs (heart rate, body temperature, systolic and diastolic blood pressure) will be summarized using descriptive statistics at baseline and at each post-baseline time point. Occurrences of systolic and diastolic blood pressure, heart rate, and body temperature readings above the pre-determined cutoff will be displayed with numbers and percentages by timepoint.

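### SAP 8.10.4 plans no table for the population-specific symptoms and no by-arm, peak or by-dose summary of vital signs, although Protocol 12.0 commits to these comparisons

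*SAP*

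**What the plan says.** **Symptoms.** Protocol 8.5 names nine symptoms, among them sensory hyperarousal. They are assessed at baseline, and exacerbations are "tracked and categorized as mild, moderate, or severe on a separate Symptoms CRF log page". Protocol 12.0 commits to a comparison: "Presence and degree of exacerbated symptoms across MDMA and placebo participant will also be examined". The SAP keeps the symptoms as a safety objective (3.3) and lists "Symptoms Specific to Population" among its safety measures (7.2). SAP 8.10.4 does not mention them again.

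**Vital signs.** Protocol 12.0 sets out to "compare pre-drug and post-drug peak blood pressure, heart rate, and body temperature during and after all experimental sessions by condition and MDMA dose". It adds a comparison of peaks between MDMA and placebo subjects and a separate analysis of dose (0, 75, 100 or 125 mg). In SAP 8.10.4, vital signs "will be summarized using descriptive statistics at baseline and at each post-baseline time point", and readings above a pre-determined cutoff are counted by time point. No treatment group, peak or dose is named.

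**The default rule.** SAP 8.0 says: "Data not subject to analysis according to this plan will not appear in any tables or graphs", and continues "but will be included in the data listings". The same section allows post-hoc exploratory analyses if they are labelled as such in the study report.

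**The concern.** Protocol 12.0 describes the trial as primarily a safety study. SAP 2.0 puts safety data first and effect size second, and says the data will decide dosing for later studies. Protocol 12.0 also says safety data will help to choose that dose. The comparisons missing from the SAP serve this purpose directly.

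The symptom log is the instrument built for this population. Protocol 2.4 bases the lower first doses on a "potential for increased sensitivity to the effects of MDMA in autistic individuals who experience sensory hyperarousal". Protocol 7.2.1 expects transient increases in blood pressure and heart rate at 125 mg. If the SAP is followed as written, the report need not contain a table of either the symptoms or the vital-sign peaks by randomized group. Any such table would be designed after the fact: subjects are unblinded individually after the six-month visit, and SAP 8.11 places the primary analysis after all subjects complete Stage 2.

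**Working it through.** The check is mainly a comparison of text. The documents state no figure that can be reproduced on this point.

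**1. Commitment against plan.**

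| Data | Protocol 12.0 | SAP 8.10.4 |
|---|---|---|
| Adverse events | Frequency tables | By Stage I treatment group |
| Spontaneously reported reactions | Number and severity, MDMA against placebo; effect of dose | By Stage I treatment group |
| SUD | Descriptive, per session | By Stage I treatment group and time period |
| C-SSRS | Not mentioned | By Stage I treatment group and time period |
| Population-specific symptoms | Presence and degree, MDMA against placebo | No analysis |
| Vital signs | Peaks by condition; separate analysis by dose | By time point only |

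The last two rows are the gap.

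**2. Amount of symptom data.** The symptoms row of Protocol Table 2 is ticked at V1 and V3 to V14, which is 1 + 12 = 13 Stage 1 visits. V1 and V3 to V5 come before any dose, so 13 − 4 = 9 visits (V6 to V14) can show an exacerbation after dosing starts. Nine graded symptoms over those nine visits have no planned table.

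**3. Whether time-point summaries can stand in for peaks.** Let x(i,j) be the reading in session i at time j. The Protocol's quantity is the peak of each session, max over j of x(i,j), summarized over sessions. For any data, the mean over i of [max over j of x(i,j)] is at least the max over j of [mean over i of x(i,j)]. The two agree only if the sessions share a time of peak. SAP 1.0 includes the maximum among its descriptive statistics, so the highest reading at each time point would be visible. The distribution of per-session peaks would not, and neither would change from the pre-drug value to the peak. Splitting the time-point tables by arm would therefore not fully deliver the Protocol's comparison.

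**4. Sessions available (Protocol Table 1).**
- Stage 1 placebo: 4 subjects × 2 = 8 sessions.
- Stage 1 MDMA: 4 at 75 mg, 4 + 4 = 8 at 100 mg and 4 at 125 mg, total 16.
- Stage 2, if all four placebo subjects enter: 4 at 75 mg and 4 at 125 mg, total 8.
- All MDMA: 16 + 8 = 24, eight per dose, matching Protocol 2.3.

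In Stage 1, 75 mg is given only at session 1 of Group 1 and 125 mg only at session 2 of Group 2. A by-dose breakdown is thus tied to group and session order.

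**5. Precision once tables by arm exist.** Take one value per subject and assume equal SDs. The 95% half-width for a difference in means is t(0.975, 10 df) × √(1/8 + 1/4) × SD = 2.228 × 0.612 × SD = 1.36 SD. The comparison is feasible but imprecise.

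**The case against.** The strongest reply is that nothing is lost. Every reading is kept per subject, the data go into the listings, labelled post-hoc work is allowed, and twelve subjects can be read by eye. That stands against any claim that a comparison with placebo is impossible. It does not answer the point that comparisons the Protocol planned have become optional and unplanned.

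Some exacerbations may also reach the adverse event tables, which are by treatment group. Protocol 8.5 lists exacerbations of symptoms recorded at medical history among the events to collect, and SAP 8.10.4 counts existing events that worsen. This stands in part. The symptoms have their own log page, so it is unclear how much would carry over.

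SAP 8.10.4 sits under 8.10, which opens with descriptive statistics by treatment group. That rule names primary, secondary and exploratory endpoints and not safety measures, so its reach is arguable.

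Four stronger readings are tempting:
- A reader might infer that the SAP pools vital signs over arms and so dilutes any rise on MDMA. The SAP leaves out the treatment group; it does not say that it pools. Any dilution figure would rest on that inference and on assumed rises.
- A reader might infer that sensitivity to MDMA goes unexamined. In Protocol 2.4, hyperarousal describes the people thought to be more sensitive. Greater sensitivity could also appear in adverse events, reactions and SUD, all planned by group.
- A reader might rank these as the trial's main risks. The Protocol does not rank them, and body temperature is covered in 7.2.3 as a slight increase, not in 7.2.1.
- General Well-being also has no analysis in SAP 8.10.4, but Protocol 12.0 promises none, so no commitment is dropped.

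**Conclusion.** The point holds as a gap between the two documents. SAP 8.10.4 omits the symptom comparison and the by-condition, peak and by-dose vital-sign comparisons to which Protocol 12.0 commits. Under SAP 8.0 the symptoms would go to data listings only, apart from any exacerbations also recorded as adverse events. The missing comparisons could still be made, but only post hoc.

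The size is best stated as what is missing: nine graded symptoms, and every per-session peak, without a planned summary by randomized group, in a trial whose first stated purpose is safety. The documents support no numerical bias. The conclusion rests on reading the by-group rule in SAP 8.10 as not covering safety measures, and on the symptom log being kept separate from the adverse event page as Protocol 8.5 describes. If either reading is wrong the gap narrows, but the peak and by-dose summaries would still be absent. The change is worth making before the analysis. The efficacy analyses are unaffected.

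**What to change.** Add to SAP 8.10.4:

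- **Symptoms.** For each of the nine symptoms, the number and percent of subjects with a post-dose exacerbation over baseline, by maximum severity and Stage 1 treatment group, with Stage 2 shown separately.
- **Vital signs.** For systolic and diastolic pressure, heart rate and temperature: the pre-drug value, the peak and the peak change, plus readings above the pre-determined cutoff, by Stage 1 treatment group and session. Add a descriptive breakdown by dose received (0, 75, 100, 125 mg).

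Present both descriptively. There are 8 against 4 subjects, and the two sessions of one subject are not independent observations.

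The cost is a few lines of SAP text and a small set of tables from data already collected. It needs no new assessments and places no burden on subjects.
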